#### 4. STUDY DESIGN

This study will be performed in healthy volunteers in a conventional 3+3 doseescalation design. There are total 4 cohorts in this study. Three cohorts (level A, B, and C) of up to 6 evaluable volunteers per cohort planned to be sequentially accrued to receive Careseng 1370 1, 2, and 3 sachets per day, 4,000 mg/sachet before meal (starting from 1 sachet, level A). One cohort (level D, modified cohort) of up to 6 evaluable volunteers per cohort will be planned to be accrued to receive 1 sachet of Careseng 1370 every other day (level D) when the dose de-escalates from level A. At least 5 days of staggering and with the investigator's judgement of no safety concern will be required to administer the next volunteer for the first three volunteers of each cohort. The staggering time starts from Day 1 of one volunteer to Day 1 of the next volunteer. Careseng 1370 should be taken around 1 hour before meal where the respective number of sachets and meals of each dose level are as follows:

- Level A (1 sachet): 1 sachet before breakfast
- Level B (2 sachets): 1 sachet before breakfast, 1 sachet before lunch
- Level C (3 sachets): 1 sachet before breakfast, 2 sachets before lunch
- Level D (1 sachet) (modified cohort): 1 sachet before breakfast on 1st, 3rd, and 5th days

Note:

1. Breakfast is defined as the first meal of the visit day while lunch is defined as the  $2^{nd}$  meal of the visit day in this study.

2. The modified cohort is the lower dose level below the starting dose level A. This cohort will be implemented when the dose de-escalates from level A.

The starting dose of Careseng 1370 (level A) is determined based on the results of the preclinical toxicity studies. Based on these data, the starting dose of Careseng 1370, 1 sachet containing 652 mg drug substance, is considered to be a safe starting dose in human. When the dose de-escalation was determined on level A, the modified cohort (level D) will be implemented. Volunteers will be followed from the start of Careseng 1370 administration up to Final visit (Day 22).

In dose-escalation, if 0 of the first 3 evaluable volunteers enrolled at a given dose level experiences DLT, then dose escalation will proceed to the next cohort of volunteers after the DSMB agrees unless it is at the highest dose level. If 0 of the first 3 evaluable volunteers enrolled at the highest dose level experiences DLT or if DLT occurs in exactly 1 of the first 3 evaluable volunteers within a given dose cohort, the cohort will

be expanded and 3 additional evaluable volunteers will be enrolled subsequently at that dose level. In the expanded cohort, if  $\leq 1$  of 6 evaluable volunteers experiences DLT, escalation to the next dose level or study completion (if at the highest dose level) will proceed after the DSMB agrees. If more than 1 evaluable volunteer ( $\geq 2$  of 3 or  $\geq$ 2 of 6 evaluable volunteers) at any given dose level experiences DLT, then no further dose escalation will occur. For such situation, unless it is at the lowest dose level of Careseng 1370 (level D), if DLT appears in 1 of 6 evaluable volunteer of the preceding cohort, then the MTD will be the preceding dose, which is essentially the highest dose cohort if  $\leq 1$  DLT was observed in all dose cohorts. If the number of evaluable volunteers is 3 in the preceding cohort, then 3 more evaluable volunteers will be added to the preceding cohort. If DLT appears in > 1 volunteer in the expanded preceding cohort, then the next lower dose cohort will be checked. If 2 of 4 or 5 evaluable volunteers experience DLT in the expanded cohort, the DSMB will determine to grant dose de-escalation based on the safety of the proceeding dose level without enrolling the next volunteer in the cohort. No dose level below pre-specified lowest dose level will be tested for this study.

No volunteer is allowed to be assigned to more than 1 dose level. All decisions for dose escalation/de-escalation will be made by the DSMB.

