#### 1.3 **Potential Risks and Benefits**

There will be no potential benefits for healthy volunteers to participate in this study.

Potential risks of Careseng 1370 are based on the toxicology findings in Sprague-Dawley (SD) rats. Possible influence on coagulation prolonged prothrombin time (PT) and activated partial thromboplastin time (APTT) was noted in both sexes of rats receiving mid- (1,350 mg/kg/day) and high-dose (2,700 mg/kg/day) for 13 weeks. But the prolonged PT and APTT were not seen at the end of recovery period in 2,700 mg/kg recovery animals. It was also noted that the mean body weights of mid- and high-dose male rats were 9.3% and 13.8% lower than that of the controls, respectively. Final mean body weight of high-dose recovery male rats was 11.8% lower than that of the controls. Final mean body weight gains of mid- and high-dose male rats were 15.7% and 23.2% lower than that of the controls. Final mean body weight gains of high-dose recovery males was 19.2% lower than that of the controls. Therefore, body weight loss and bleeding prolonged are possible risks that subjects in this study may experience.

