#### 2. OBJECTIVES AND ENDPOINTS

#### 2.1 Objectives

#### **Primary objective:**

The primary study objective is to explore the safety and tolerability profiles of Careseng 1370 as single agent based on DLT observed in healthy volunteers. The results will be employed for future study to determine the MTD of Careseng 1370 to treat chemotherapy-induced myelosuppression in advanced non-small cell lung cancer (NSCLC) patients.

DLT is defined as any  $\geq$  Grade 2 adverse event from Day 1 to Day 10 (DLT observation period), causally at least possibly related to Careseng 1370 administration as judged by the investigator. The grading system applied in this study is "Guidance for Industry: Toxicity Grading Scale for Healthy Adult and Adolescent Volunteers Enrolled in Preventive Vaccine Clinical Trials" (Appendix 1), issued by United States Food and Drug Administration in September 2007. The definition of Grade 5 (death) was added to this grading system as it was not defined in the guidance (Section 8.2 and Appendix 1).

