#### **3.** STUDY POPULATION

#### 3.1 Volunteers Enrollment

In design of traditional 3+3 paradigm with four candidate dose levels, the number of evaluable healthy volunteers will be up to 24.

Note: A volunteer is considered evaluable if he/she

1. receives any Careseng 1370, and

2. experiences DLT OR completes DLT observation period with at least 80% of study drug compliance and has exposed to Careseng 1370 for at least 4 days (level A, B, and C), OR completes DLT observation period with 100% of study drug compliance (level D).

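### After 1 DLT in 3, nothing spaces volunteers 4, 5 and 6, so the stop at 2 DLTs in 4 or 5 can come too late to spare any of them

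*Protocol*

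**What the plan says.** The staggering rule is in the Study Design row of the Protocol Summary and in Section 4. An interval of at least 5 days, counted from Day 1 of one volunteer to Day 1 of the next, together with the investigator's judgement that there is no safety concern, "will be required to administer the next volunteer for the first three volunteers of each cohort".

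The expansion rule in Section 4 applies after exactly 1 DLT in the first 3 evaluable volunteers, or after 0 in 3 at the highest level. Then "3 additional evaluable volunteers will be enrolled subsequently at that dose level". No interval among these three is given.

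The early stop follows in the same section: "If 2 of 4 or 5 evaluable volunteers experience DLT in the expanded cohort, the DSMB will determine to grant dose de-escalation", and it does so "based on the safety of the proceeding dose level without enrolling the next volunteer in the cohort". More than 1 DLT "at any given dose level experiences DLT, then no further dose escalation will occur".

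Two definitions fix the timing. Under Section 2.1, a DLT is a Grade 2 or higher event "from Day 1 to Day 10 (DLT observation period), causally at least possibly related to Careseng 1370 administration as judged by the investigator". Under Section 3.1, a volunteer at levels A to C without a DLT becomes evaluable only if he or she "completes DLT observation period with at least 80% of study drug compliance" and has at least 4 days of exposure; level D requires full compliance.

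**The concern.** The early stop acts only on people who have not yet been dosed. To protect anyone it needs time between volunteers 4 and 5 and between 5 and 6, and the stagger rule leaves out exactly these volunteers.

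After 1 DLT in 3, one further DLT makes 2 or more in 6 certain, and escalation is then barred. Dosing volunteer 5 or 6 after that point cannot alter the escalation result, but it exposes another healthy person. Section 1.3 is explicit: "There will be no potential benefits for healthy volunteers to participate in this study". The plan requires spacing before any DLT has been seen at a level and stops requiring it once one has been seen, which is hard to justify.

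What is at stake is avoidable exposure of healthy volunteers. Escalation and MTD decisions are not affected.

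**Working it through.** **No stated figure to reproduce.** The plan gives no number for this point. The related count, 4 cohorts × 6 = 24 evaluable volunteers, agrees with Section 10.1.

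**Who is held back by the text**
- Volunteers 1 to 3: spaced by the stagger rule.
- Volunteer 4: held in effect, because expansion needs the outcome of the first 3 evaluable volunteers, and each outcome needs a DLT or completion of Days 1 to 10. The stagger sentence can also be read as covering the step from 3 to 4.
- Volunteers 5 and 6: no interval or check on either reading. The withdrawal criteria (Section 3.4) and discontinuation rules (Section 4.3) act on individual volunteers and set no spacing.

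**Inputs**
- From the protocol: a 5-day gap, a DLT window of Days 1 to 10, and a cohort with 1 DLT in its first three.
- Assumed, because the documents give neither: p, the DLT probability per further volunteer (0.10, 0.20, 1/3, 0.50), and f, the share of DLTs with onset by Day 5 (1, 0.5, 0).

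**Same-day start.** All three have had a first dose before any of them can have a DLT. Spared = 0 at every p. The chance of 2 or more DLTs in 6 is then 1 − (1 − p)³ = 27%, 49%, 70%, 88%.

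**5-day gaps.** Volunteer 5 starts on Day 6 of volunteer 4. Volunteer 6 starts on Day 11 of volunteer 4 and Day 6 of volunteer 5. The expected number spared among volunteers 5 and 6 has three parts:
- volunteer 4 has an early DLT, sparing both: 2pf
- volunteer 4 has a late DLT, sparing volunteer 6: p(1 − f)
- volunteer 4 has none and volunteer 5 has an early DLT, sparing volunteer 6: (1 − p)pf

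The sum is p + pf + (1 − p)pf. With f = 1 it is 3p − p²; for example, at p = 0.20, 0.60 − 0.04 = 0.56. With f = 0 it is p.

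**Short, unrequired gaps of g days (g up to 5), onset uniform over Days 1 to 10.** With a = pg/10, spared = a + 2a + (1 − 2a)a = 4a − 2a². At g = 5 this equals the f = 0.5 result, as it should.

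| Volunteers spared, given 1 DLT in 3 | p = 0.10 | 0.20 | 1/3 | 0.50 |
|---|---|---|---|---|
| Same-day start | 0 | 0 | 0 | 0 |
| 1 day apart | 0.04 | 0.08 | 0.13 | 0.20 |
| 2 days apart | 0.08 | 0.16 | 0.26 | 0.38 |
| 5 days, f = 0 | 0.10 | 0.20 | 0.33 | 0.50 |
| 5 days, f = 0.5 | 0.20 | 0.38 | 0.61 | 0.88 |
| 5 days, f = 1 | 0.29 | 0.56 | 0.89 | 1.25 |

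**Per cohort entered.** Multiply by the chance of exactly 1 DLT in 3, which is 3p(1 − p)² = 0.24, 0.38, 0.44, 0.38. With 5-day gaps this gives:
- f = 1: 0.07, 0.21, 0.40, 0.47
- f = 0.5: 0.05, 0.15, 0.27, 0.33
- f = 0: 0.02, 0.08, 0.15, 0.19

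For each onset assumption these are upper bounds, since the DSMB still has to decide.

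**Expansion after 0 DLTs in 3.** Two in 4 is impossible, and 2 in 5 needs a DLT in both volunteers 4 and 5. At most p² = 0.01, 0.04, 0.11, 0.25 is spared, so spacing matters little there.

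**The case against.** The strongest reply is that a same-day start runs against the rule's own wording. A stop at 2 in 4 or 5 that refers to the next enrolment has no effect unless entry is one at a time, so sequential entry was probably intended. That is fair. But the wording gives no minimum interval and no check, and starts one or two days apart recover little of the benefit. For the first three volunteers the protocol states both the number of days and how to count them.

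Second, mandatory staggering only for the first three at a level, then reliance on the DSMB and the investigator, is a defensible choice. The amendment history (Section 14, version 3.0) records that the DSMB granted the added special scenarios. That does not show that spacing was considered, and the DSMB cannot undo a first dose. It or the investigator could halt remaining doses, but the protocol does not say so for volunteers without a DLT.

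Third, exposure is not harm. Multiplying the per-cohort figures by p gives DLTs avoided per cohort entered of about 0.005, 0.03, 0.09 and 0.16 at f = 0.5. A DLT can be a Grade 2 event. The top dose is 3 × 652 = 1,956 mg, or 32.6 mg/kg at 60 kg, about 30% of the 108.8 mg/kg human equivalent of the NOAEL (Section 1.2.2). Nothing in the documents supports the higher values of p. Extra volunteers also add adverse event and PK data. All this stands and limits the weight of the point.

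Last, a 5-day gap covers only half of the DLT window, and the SAP is dated after the expected end of the trial. Both are true. The protection is partial, and for this trial mainly reporting may remain.

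**Conclusion.** The concern holds, as a minor one. The text leaves volunteers 4, 5 and 6 unspaced, and these are the people the early stop is meant to spare. With a same-day start it spares none of them. Extending the 5-day gap would spare between 0.10 (p = 0.10, no DLT by Day 5) and 1.25 (p = 0.50, all by Day 5) of volunteers 5 and 6 in a cohort with 1 DLT in its first three, or between 0.02 and 0.47 per cohort entered.

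The textual gap is certain. Its size rests on assumed DLT probabilities and onset times, and on comparison with a same-day start; any spacing the site already uses reduces the gain.

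**What to change.** In the Study Design row of the Protocol Summary and in Section 4, state that in a cohort expanded after 1 DLT in the first three evaluable volunteers, the same stagger (at least 5 days, Day 1 to Day 1, with the investigator's no-safety-concern judgement) also applies between volunteers 4 and 5 and between 5 and 6. Add that once 2 DLTs have occurred in a cohort, nobody further is dosed at that level until the DSMB has decided. Spacing after 0 DLTs in 3 can stay optional.

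The cost is wording plus two 5-day gaps, about 10 days per cohort expanded after 1 in 3. Per cohort entered that averages 10 × 3p(1 − p)² = 2.4, 3.8, 4.4 and 3.8 days at the four values of p. No wait is added before volunteer 4, and no volunteers or procedures are added.

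SAP Section 3 expected the last subject to finish in March 2022. If enrolment is complete, report the actual start dates of volunteers 4 to 6 in any cohort expanded after 1 in 3; SAP listing 16.2.1.2 already holds the first treatment date. Carry the wording into any later protocol that reuses this scheme. The next study named is in NSCLC patients, where the spacing logic still applies but the no-benefit argument does not transfer directly.

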## 1.2.2 Rationale for Doses Selected

Based on the preclinical toxicity study, no-observed-adverse-effect level (NOAEL) of DS-1370 is determined as 675 mg/kg/day in rats of both genders, leading to human equivalent dose (HED) of 675/6.2 = 108.8 mg/kg/day. Considering choosing a safety factor of 10, the maximum recommended starting dose (MRSD) is 10.88 mg/kg/day, equivalent to around 653 mg/day for a 60-kg adult. The pharmacology data indicates that administration of DS-1370 536 mg/kg and 1,072 mg/kg (but not 268 mg/kg) daily are efficacious in treating myelosuppression caused by docetaxel and cisplatin in mice. The HED (divided by 12.3) based on 536 mg/kg is 43.58 mg/kg/day (2,614.63 mg/day for a 60-kg adult). Each Careseng 1370 sachet will be around 4,000 mg in weight containing powder of 652 mg DS-1370 (16.3% w/w) plus 3,348 mg of excipients (83.7% w/w). The MRSD will be one sachet per day and the anticipated therapeutic dose (ATD) range will be 4 to 8 sachets per day. One, two, and three sachets of Careseng 1370 per day (level A, B, and C) are therefore selected at Sponsor's discretion for this study. Consideration of

unexpected drug effects on human body, one modified cohort (level D) is planned as the lower dose level below the starting dose level A. The modified cohort (level D) will be implemented when the dose de-escalates from level A.

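### The MTD clause contradicts itself and leaves no supportable MTD result for a trial in which Level C passes the DLT limit

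*Protocol*

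**What the plan says.** Protocol Section 4 has Levels A, B and C "planned to be sequentially accrued to receive Careseng 1370 1, 2, and 3 sachets per day", so Level C is the top of the escalation. Three of its rules matter here.

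- **Stopping.** If at least 2 of 3 or at least 2 of 6 evaluable volunteers at any level have a DLT, "then no further dose escalation will occur".
- **MTD.** The next sentence is introduced as applying to that stopping situation. It first sets a requirement: "if DLT appears in 1 of 6 evaluable volunteer of the preceding cohort". Where this requirement is met, it draws the conclusion: "then the MTD will be the preceding dose, which is essentially the highest dose cohort if" no more than one "DLT was observed in all dose cohorts".
- **Passing.** For an expanded cohort with at most 1 DLT in 6, "escalation to the next dose level or study completion (if at the highest dose level) will proceed after the DSMB agrees". This rule does not mention an MTD.

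The Protocol Summary repeats the paragraph. In the text available to me, its copy of the MTD sentence shows a strict inequality where Section 4 has at most 1. That may be a PDF-reading artefact, and nothing below depends on it.

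Protocol Section 10.2.1 says the MTD decision will rest on the DLTs of evaluable subjects. SAP Section 1.2 defines an MTD-Evaluable Population for determining the MTD. Neither document provides for the outcome that no MTD was reached.

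**The concern.** An MTD is informative when a higher dose has been tried and found to exceed the tolerability limit. The clause attaches the label to the top cohort on the condition that no cohort exceeded the limit, which is the case in which the trial has not located a maximum. The clause also sits inside a sentence about trials where some level did exceed it.

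At stake is what the study report says if Levels A, B and C all pass. Following the words, it would call 3 sachets per day the maximum tolerated dose without any observation above that dose. Following the structure of the sentence, the report's authors would have no rule and would have to choose one after seeing the data.

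**Working it through.** **1. The conditions side by side.**

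| Part of the rule | Condition |
|---|---|
| Situation the MTD sentence governs | at least one level with 2 or more DLTs |
| Gloss inside that sentence | every level with 1 or fewer DLTs |

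Each is the negation of the other, so the gloss can never apply within the sentence that contains it. Two readings remain:

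- *Face value:* the gloss applies when all cohorts have at most 1 DLT. Level C is then called the MTD.
- *Confined to the stopping situation:* the gloss is empty. A trial in which Level C passes ends in study completion, with no stated MTD result.

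Both readings fail in the same event: no tested level exceeds the limit.

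**2. The plan's own figure.** The maximum number of evaluable volunteers is 4 cohorts × 6 = 24, which reproduces the protocol. No number in the plan is disputed. The figure shows only that each level is judged on at most 6 volunteers.

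**3. How likely is that event?** Let p be the true DLT probability at a level. The documents give no DLT rates, so every p below is an assumption.

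- Level A or B passes with 0/3, or with 1/3 followed by 0/3: (1−p)³ + 3p(1−p)² × (1−p)³.
- Level C is expanded even after 0/3, so it passes with at most 1 of 6: (1−p)⁶ + 6p(1−p)⁵.
- P(no level exceeds the limit) is the product over A, B and C.

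Worked example, 5/10/20%:

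- A: 0.8574 + 0.1354 × 0.8574 = 0.973
- B: 0.729 + 0.243 × 0.729 = 0.906
- C: 0.2621 + 0.3932 = 0.655
- Product: 0.973 × 0.906 × 0.655 = 0.578

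| Assumed DLT rate at A/B/C | P(no level exceeds the limit) |
|---|---|
| 1/1/1% | 0.996 |
| 5/5/5% | 0.917 |
| 10/10/10% | 0.727 |
| 20/20/20% | 0.329 |
| 33/33/33% | 0.068 |
| 1/2/5% | 0.962 |
| 2/5/10% | 0.858 |
| 5/10/20% | 0.578 |
| 5/15/30% | 0.333 |

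**4. What the data would then say about Level C.** Exact (Clopper-Pearson) two-sided 95% limits:

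- 0/6: upper limit 1 − 0.025^(1/6) = 45.9%; interval 0 to 45.9%.
- 1/6: the upper limit solves (1−p)⁵(1+5p) = 0.025, giving p = 64.1%; interval 0.4% to 64.1%.

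**5. A related gap.** The MTD sentence requires exactly 1 DLT in 6 in the preceding cohort, while the passing rule accepts at most 1 in 6. A preceding cohort that escalated on 0/3, was later expanded, and finished with 0/6 meets the passing rule but has no stated MTD result.

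**The case against.** The strongest reply is that the sentence is badly drafted rather than wrong in intent. It is confined to trials with 2 or more DLTs at some level, and the rule for a passing top level declares no MTD. So it is not settled that the protocol names the top dose as the MTD. This stands, and is why the point is put as a contradiction with two readings. It does not remove the problem, because the second reading leaves the outcome undefined. The clause may also have been meant as the highest cohort with at most 1 DLT. On that meaning too, Level C is labelled the MTD with nothing above it tested.

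A reader might draw four stronger inferences that the documents do not support.

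- *That the clause contradicts the primary objective.* Section 2.1 does say "The results will be employed for future study to determine the MTD of Careseng 1370", but the sentence goes on to NSCLC patients. An MTD in patients is a different quantity from one in healthy volunteers.
- *That the cap of 3 sachets has no safety basis.* Section 1.2.2 attributes the choice to the sponsor's discretion. However, the dietary calcium allowance in Section 3.5 falls from 1,730 to 960 to 200 mg/day across A, B and C, and the amendment history gives excipient overdose as the reason for removing a 4-sachet level. The documents support only that the cap was not set by observed DLTs.
- *That the label puts the trial in conflict with its therapeutic range.* Section 1.2.2 says "the anticipated therapeutic dose (ATD) range will be 4 to 8 sachets per day". That range lies above every tested dose whatever Level C is called.
- *That the primary result changes.* The primary endpoint is the incidence of AEs and SAEs (Section 2.2.1). The SAP has no MTD results table, and its Table 14.3.1.4 would show the Level C DLT count in any case.

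It is also fair to say that wide intervals are a property of six volunteers and would be the same under either label.

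**Conclusion.** The MTD clause is self-contradictory as written. At face value it gives Level C a label that the data could not support. Confined to its governing condition, it leaves the plan without an MTD outcome in a trial where Level C passes, although both documents say an MTD will be decided.

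The affected outcome has probability 0.92 to 0.73 for a common DLT rate of 5% to 10%, 0.58 for 5/10/20%, and 0.07 for a common 33%. Over all the profiles tried it runs from 0.07 to 0.996. These figures rest entirely on assumed rates and on independent volunteers. They show that the outcome is the likely one if the product is well tolerated, and do not predict this trial. In that outcome the 95% upper limit on the Level C DLT rate is 45.9% (0/6) or 64.1% (1/6).

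This is a defect in the definition and reporting of a stated conclusion. It does not affect the primary endpoint, and a correction is worthwhile because it costs so little.

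**What to change.** Delete the gloss about the highest dose cohort from Section 4 and the Protocol Summary. Add a separate sentence to the protocol, and use the same wording in the SAP and the study report:

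> An MTD is declared only if a higher tested level exceeded the DLT limit. If no tested level exceeded it, the MTD was not reached, and Level C is reported as the highest tested dose that met the DLT criterion, with its DLT count and exact 95% CI.

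In the same paragraph, reconcile the preceding-cohort condition (exactly 1 of 6) with the passing rule (at most 1 of 6), so that the text states what is concluded after 0 of 6.

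The SAP is dated 08-SEP-2022, after the March 2022 date it gives for the last subject's expected exit. If the protocol can no longer usefully be amended, the SAP and report are the places to make the change.

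The cost is a few sentences. Dosing, escalation, sample size and data collection are unchanged. The downside for the sponsor is a slightly less favourable stated conclusion if all levels pass.
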